11.1.4 Relatedness

AEs will be categorized according to the likelihood that they are related to the study drug(s).

To ensure consistency of AE and SAE causality assessments, site investigators should apply the following general guideline:

Yes

There is a plausible temporal relationship between the onset of the AE and administration of ipatasertib, and the AE cannot be readily explained by the subject's clinical state, inter-current illness, or concomitant therapies; and/or the AE follows a known pattern of response to ipatasertib; and/or the AE abates or resolves upon discontinuation of atezolizumab or dose reduction and, if applicable, reappears upon re- challenge.

No

Evidence exists that the AE has an etiology other than the ipatasertib (e.g., preexisting medical condition, underlying disease, inter-current illness, or concomitant medication); and/or the AE has no plausible temporal relationship to ipatasertib administration (e.g., cancer diagnosed 2 days after first dose of Ipatasertib).

Expected adverse events are those adverse events that are listed or characterized in the current Investigator Brochure (IB).

Unexpected adverse events are those not listed in the current IB or not identified. This includes adverse events for which the specificity or severity is not consistent with the description in the package insert or IB.

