11.2.3 Serious Adverse Events (SAEs)

11.2.3.1 Site Requirements for Reporting SAEs to Big Ten CRC Administrative Headquarters

- SAEs will be reported from time of study drug administration until 30 days after discontinuation of study drug(s) or until a new anti-cancer treatment starts, whichever occurs first.
- SAEs will be reported on the SAE Submission Form and entered in the SAE tab in the EDC system.
- SAEs include events related and unrelated to the study drug(s).
- All SAEs will be recorded in the subject's medical record and on the appropriate study specific eCRF form within the EDC system.
- All SAEs regardless of relation to study drug will be followed until resolution to \leq Grade 1 or baseline and/or deemed clinically insignificant and/or until a new anti-cancer treatment starts, whichever occurs first.

For SAEs and AESIs assessed as at least possibly related to the study drug(s) or assessed as unknown relation, the site will submit the completed SAE Submission Form (see Documents/Info tab in the EDC) to Big Ten CRC AHQ within **1 business day** of discovery of the event. The form will be sent electronically to Big Ten CRC AHQ at [contact]. The site investigator is responsible for informing the IRB and/or other local regulatory bodies of the SAE as per local requirements.

The original copy of the SAE Submission Form and the email correspondence must be kept within the study file at the study site.

Once the SAE has resolved, sites must electronically submit a follow up SAE Submission Form within a reasonable timeframe to Big Ten CRC AHQ at [contact].

SAEs assessed as unrelated to study drug will entered in to the EDC within 30 days of awareness of the event.

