12.7.2 Phase II (Neoadjuvant Cohort)

In the Phase II neoadjuvant cohort, if after 9 evaluable patients there are no patients with exceptional response (defined as pCR or MRD), accrual will halt due to lack of efficacy. Accrual will not pause while the 9th patient is on therapy, so additional patients may accrue prior to pathologic evaluation of the 9th radical prostatectomy.

For the Phase II neoadjuvant cohort, an additional *early stopping rule for safety* will also be followed throughout the duration of the study. If, at any time, 2 or more patients experience a delay in time to prostatectomy of >28 days after the final dose of ipatasertib (i.e., a delay of > 1 week beyond the allowed timeline of 7-21 days) *due to an ipatasertib-related AE*, the study and all study treatment will be stopped. An ipatasertib-related AE is defined as an AE that is possibly, probably, or definitely related to ipatasertib. Should the study stop early, discussion of reopening the study using modified ipatasertib treatment regimens may be considered after discussion between the PI and Genentech, and after approval by the DSMC.

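### Sites are told to judge relatedness as Yes or No (11.1.4), while the Phase II safety stopping rule (12.7.2) and expedited SAE reporting (11.2.3.1) use graded terms, with no mapping between them

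*Combined protocol and SAP*

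**What the plan says.** Three sections of the combined protocol and SAP depend on whether an AE is related to treatment.

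- **12.7.2, Phase II safety stopping rule.** The trigger reads: "If, at any time, 2 or more patients experience a delay in time to prostatectomy of >28 days after the final dose of ipatasertib", where the cause is an ipatasertib-related AE. The study and all study treatment then stop. The section supplies its own definition: "An ipatasertib-related AE is defined as an AE that is possibly, probably, or definitely related to ipatasertib".
- **11.2.3.1, SAE reporting by sites.** The route of 1 business day applies as follows: "For SAEs and AESIs assessed as at least possibly related to the study drug(s) or assessed as unknown relation". The slower route is: "SAEs assessed as unrelated to study drug will entered in to the EDC within 30 days of awareness of the event".
- **11.1.4, Relatedness.** It opens by promising categories by likelihood and then instructs sites: "To ensure consistency of AE and SAE causality assessments, site investigators should apply the following general guideline". Two categories follow, Yes and No. One sufficient ground for No is: "Evidence exists that the AE has an etiology other than the ipatasertib".

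Possible, probable, definite and unknown are not defined anywhere in the document, and no section says how they correspond to Yes and No.

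**The concern.** Two safety mechanisms take as input a graded judgement that the protocol's only causality guideline does not produce. The mismatch also has a direction. In ordinary use, a possibly related event has plausible timing and a competing explanation. Under 11.1.4, evidence of a competing explanation is a ground for No. Every man also receives ADT and darolutamide, so competing attributions will not be rare.

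If an assessment of No is carried through to 12.7.2, an event that the rule's own definition would count may be left out, and the rule needs only two patients to fire. If it is carried through to 11.2.3.1, an SAE loses expedited handling.

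**Working it through.** **Step 1. Set the terms side by side.**

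| Section | Use | Terms |
|---|---|---|
| 11.1.4 | Site causality assessment of AEs and SAEs | Yes, No |
| 12.7.2 | Stopping rule, counted by patient | possibly, probably, definitely |
| 11.2.3.1 | Report in 1 business day | at least possibly, unknown |
| 11.2.3.1 | Data entry within 30 days | unrelated |

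12.7.2 and 11.2.3.1 also differ from each other: unknown relation triggers expedited reporting but is not part of the stopping rule.

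**Step 2. Find which events fall between the scales.** 11.1.4 joins its grounds with and/or. The grounds for Yes are:

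- (a) plausible timing, and not readily explained by clinical state, intercurrent illness or other therapy;
- (b) a known pattern of response to ipatasertib;
- (c) abatement on discontinuation or dose reduction.

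The grounds for No are:

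- (d) evidence of another cause;
- (e) no plausible timing.

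Take an AE with plausible timing and evidence of another cause that readily explains it. It is not typical of ipatasertib and does not abate. It fails (a), (b) and (c) and meets (d), so it is assessed No. In the ordinary sense of the word it can still be possibly related, so 12.7.2 and 11.2.3.1 would capture it. An AE that meets (b) or (c) can be assessed Yes despite the competing cause. I leave those events out, although 11.1.4 does not say which answer prevails when a ground for each is met.

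**Step 3. Follow such an event through the plan.**

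- *Non-serious AE that delays surgery.* The sponsor-investigator's relatedness review in 11.2.3.4 starts from an SAE Submission Form, so it does not cover this event.
- *SAE.* The site deadline moves from 1 business day to EDC entry within 30 days, and reporting to the two companies becomes monthly (11.2.3.2, 11.2.3.3).

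**Step 4. Illustrate the effect on the stopping rule.** The plan states no operating characteristics for this rule, so there is no figure to reproduce. Inputs:

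- n = 20, the planned Phase II enrolment (12.3);
- threshold of 2 patients (12.7.2);
- q, the true proportion of men with a qualifying delay from an at least possibly related AE: assumed;
- m, the share of those assessed No and therefore not counted: assumed.

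With p = q(1 − m), P(at least 2 counted) = 1 − (1 − p)^20 − 20p(1 − p)^19.

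- q = 0.10, m = 0: p = 0.10; 1 − 0.1216 − 0.2702 = 0.608
- q = 0.10, m = 0.30: p = 0.07; 1 − 0.2342 − 0.3526 = 0.413
- q = 0.10, m = 0.50: p = 0.05; 1 − 0.3585 − 0.3774 = 0.264
- q = 0.20, m = 0: p = 0.20; 1 − 0.0115 − 0.0576 = 0.931
- q = 0.20, m = 0.25: p = 0.15; result 0.824
- q = 0.20, m = 0.50: p = 0.10; result 0.608

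With the 17 evaluable patients in place of 20, the figure falls from 0.518 to 0.208 at q = 0.10 and from 0.882 to 0.518 at q = 0.20, each for m = 0.50.

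The sensitivity comes from the low threshold. If exactly two men truly qualify, the rule fires only when both are counted. That has probability (1 − m)²: 0.49 at m = 0.30 and 0.25 at m = 0.50.

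**The case against.** The case on the other side has five parts.

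1. **The forms are not shown.** 11.1.4 is called a general guideline. The eCRF and SAE Submission Form are not in the documents, and 11.2.3.1 itself speaks of events assessed as of unknown relation. A reader might infer that sites can record only Yes or No and that unknown cannot be entered. The documents do not support that. They show what the protocol text defines, not what the data fields allow. This stands.
2. **12.7.2 carries its own definition.** It does not point to 11.1.4, so whoever applies it could ask directly whether the AE was at least possibly related, whatever the site entered. This stands in part. The section names neither the person who makes that judgement nor the record it is made from, and the only instruction to sites on causality is Yes or No.
3. **The other grounds for Yes rescue many events.** Diarrhea, rash, hyperglycemia and fatigue are described in section 6 as seen with ipatasertib, and events of these kinds can be Yes on the known-pattern ground. This stands and narrows the exposed group to the one in Step 2.
4. **There are backstops.** 11.2.3.1 says that SAEs, related or not, go on the SAE form. 11.2.3.4 has the sponsor-investigator reassess relatedness on a summary of that form. 13.1 and 13.2 provide DSMC review, including after SAEs, and monthly site calls in Phase II. This stands for SAEs, which are recorded in any case; what they can lose is speed. None of these steps guarantees a relatedness review of a non-serious AE that delays surgery.
5. **The rates are assumed.** Neither the delay rates nor the shares assessed No have a source in the documents. This stands, and the probabilities serve only as illustration.

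**Conclusion.** The inconsistency is real and should be corrected. 11.1.4, 11.2.3.1 and 12.7.2 use relatedness terms that the protocol does not reconcile, and a definable group of events can be assessed No under the first although the other two intend to capture them. For SAEs the cost is a move from 1 business day to as long as 30 days at the site. For the stopping rule, one event can decide whether it fires.

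The illustrative loss is from 0.61 to 0.41 or 0.26 at a 10% rate of qualifying delays (30% or 50% assessed No), and from 0.93 to 0.61 at a 20% rate (50% assessed No). These figures assume 20 men with independent outcomes, the ordinary meaning of possibly related, and a count that follows the site's Yes or No. A reader might go further and conclude that possibly related events will go uncounted. The documents support only that they can. With the forms unseen, confidence in the practical effect is medium; the conflict in the text is plain.

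**What to change.** Either of two changes is enough.

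- **One scale.** Put the terms that 12.7.2 and 11.2.3.1 already use into 11.1.4, define each, and use them in all three sections.
- **An explicit mapping.** Keep Yes and No, and state in 11.1.4 that possible, probable and definite count as Yes for 12.7.2, and that those three plus unknown count as Yes for 11.2.3.1, even when another cause is also plausible.

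In both cases, make the eCRF and the SAE Submission Form match. The same edit can correct two slips in 11.1.4: it is written for ipatasertib alone although 11.2.3.1 refers to the study drugs in general, and it names atezolizumab, which is not a drug in this trial.

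The cost is a short edit to one section and a check of two forms. The price is slightly more expedited reports and a slightly more sensitive stopping rule. The two-patient threshold and the 28-day limit are untouched.

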13. TRIAL MANAGEMENT

13.1 Data and Safety Monitoring Plan (DSMP)

This study will be conducted in compliance with the Data Safety Monitoring Plan (DSMP) of the Robert H. Lurie Comprehensive Cancer Center of Northwestern University.

BTCRC AHQ oversight activities include:

- Review and processing of all adverse events requiring expedited reporting as defined in the protocol
- Provide trial accrual progress, safety information, and data summary reports to the sponsor-investigator
- Submit data summary reports to the lead institution DSMC and attend DSMC reviews:
 - during the Phase I portion of the study, monthly to present safety summary reports
 - during the Phase II neoadjuvant portion of the study, as applicable: following any reports of protocol deviations that meet IRB expedited reporting requirements, continued non-compliance or SAEs; and overall study data delinquency that exceeds 10% incomplete forms or sites with data delinquency that are not responding sufficiently to the BTCRC AHQ data delinquency escalation process
 - throughout the study, semi-annual comprehensive DSMC review

- During the Phase I portion of the study there will be weekly safety calls with all participating institutions. During the neoadjuvant portion of the study there will be monthly calls with all participating institutions

13.2 Robert H. Lurie Comprehensive Cancer Center's Data Safety Monitoring Committee

BTCRC AHQ will provide the following for the Robert H. Lurie Comprehensive Cancer Center's DSMC to review:

- Adverse event/ serious adverse event summary report
- Monitoring reports
- Audit results if applicable
- Study accrual patterns
- Data delinquency
- Protocol deviations
- Annual report, prior to submission to the FDA (if the study is under an IND).

The Robert H. Lurie Comprehensive Cancer Center's DSMC will conduct a comprehensive study review semi-annually, based on the date the study was originally opened with NU. Ad hoc reviews may be performed as necessary to ensure patient safety and data integrity. Documentation of DSMC reviews will be provided to sponsor-investigator and BTCRC AHQ. Issues of immediate concern by the DSMC will be brought to the attention of the sponsor-investigator and other regulatory bodies as appropriate. The sponsor-investigator will work with BTCRC AHQ to address the DSMC's concerns.

Link to the Robert H. Lurie Comprehensive Cancer Center's Data and Safety Monitoring Plan:
<https://www.cancer.northwestern.edu/docs/research/data-safety-monitoring-plan.pdf>

13.3 DSMC Review of Safety Data

The Sponsor Investigator and the study team will review all available safety data prior to making dose de-escalation decisions. Once a decision has been reached, the official decision and the supporting safety data will be submitted to the NU DSMC. Treatment of additional subjects may not proceed until the DSMC approves the dosing decision for the next stage. This process will also apply during any interim analyses.

13.4 Data Quality Oversight Activities

Remote validation of the EDC system data will be completed on a continual basis throughout the life cycle of the study. Automated edit check listings will be used to generate queries in the EDC system and transmitted to the site to address in a timely fashion. Corrections will be made by the study site personnel.

The level of risk attributed to this study requires high-intensity monitoring, as outlined in the DSMP. This study will be monitored in accordance with the study phase and risk level with oversight from the NU Data and Safety Monitoring Committee. For cause visits may occur as necessary. The database will be monitored regularly in house and if significant discrepancies arise, an onsite monitoring visit will be scheduled. Monitoring will be conducted by adequately qualified HCRN employees. During onsite monitoring visits, source documents will be reviewed for verification of agreement with data entered into the EDC system. It is important for the site investigator and their relevant personnel to be available

for a sufficient amount of time during the monitoring visits or audit, if applicable. The site investigator and institution guarantee access to source documents by Big Ten CRC AHQ or its designee.

The trial site may also be subject to quality assurance audit by Bayer or Genentech Inc or their designee as well as inspection by appropriate regulatory agencies.

13.5 Compliance with Trial Registration and Results Posting Requirements

Under the terms of the Food and Drug Administration Modernization Act (FDAMA) and the Food and Drug Administration Amendments Act (FDAAA), the sponsor-investigator of the trial is solely responsible for determining whether the trial and its results are subject to the requirements for submission to the Clinical Trials Data Bank, <http://www.clinicaltrials.gov>. All results of primary and secondary objectives must be posted to CT.gov within a year of completion. The sponsor-investigator has delegated responsibility to Big Ten CRC AHQ for registering the trial and posting the results on clinicaltrials.gov. Information posted will allow subjects to identify potentially appropriate trials for their disease conditions and pursue participation by calling a central contact number for further information on appropriate trial locations and study site contact information.

14. DATA HANDLING AND RECORD KEEPING

14.1 Data Management

Big Ten CRC AHQ will serve as the Clinical Research Organization for this trial. Data will be collected through a web-based clinical research platform compliant with Good Clinical Practices and Federal Rules and Regulations. Big Ten CRC AHQ personnel will coordinate and manage data for quality control assurance and integrity. All data will be collected and entered into the EDC system by study site personnel from participating institutions.

14.2 Case Report Forms and Submission

Generally, clinical data will be electronically captured in the EDC system and correlative results will be captured in the EDC system or other secure database(s). If procedures on the study calendar are performed for standard of care, at minimum, that data will be captured in the source document. Select standard of care data will also be captured in the EDC system, according to study-specific objectives. Please see the Data and Safety Oversight Process (DSOP) guidelines for further details.

The completed dataset is housed at Big Ten CRC AHQ and is the sole property of the sponsor-investigator's institution. It should not be made available in any form to third parties, except for authorized representatives of appropriate Health/Regulatory Authorities, without written permission from the sponsor-investigator and Big Ten CRC AHQ. After the initial publication, the complete data set will be available to all Big Ten CRC institutions.

14.3 Record Retention

To enable evaluations and/or audits from Health Authorities/Big Ten CRC AHQ, the site investigator agrees to keep records, including the identity of all subjects (sufficient information to link records; e.g., hospital records), all original signed informed consent forms, copies of all source documents, drug diaries, and detailed records of drug disposition. All source documents are to remain in the subject's file

and retained by the site investigator in compliance with local and federal regulations. No records will be destroyed until Big Ten CRC AHQ confirms destruction is permitted.

14.4 Confidentiality

There is a slight risk of loss of confidentiality of subject information. All records identifying the subjects will be kept confidential and, to the extent permitted by the applicable laws and/or regulations, will not be made publicly available. Information collected will be maintained on secure, password protected electronic systems. Paper files that contain personal information will be kept in locked and secure locations only accessible to the study site personnel.

Subjects will be informed in writing that some organizations including the sponsor-investigator and his/her research associates, Big Ten CRC AHQ, Bayer, Genentech Inc, IRB, or government agencies, like the FDA, may inspect their medical records to verify the information collected, and that all personal information made available for inspection will be handled in strictest confidence and in accordance with local data protection laws.

If the results of the study are published, the subjects's identity will remain confidential.

14.5 Publication Policy

All potential publications and/or data for potential publications (e.g., manuscripts, abstracts, posters, clinicaltrials.gov releases, etc.) must be approved in accordance with the Data Safety Monitoring Committee (DSMC) Data Release Policies and Processes. The investigator is expected to use only DSMC-approved data and statistical analyses any time they are disseminating trial data. The investigator must send a copy of the draft communication materials (e.g., abstract, poster, manuscript, etc.) to the study's biostatistician and assigned Quality Assurance Manager (QAM) [\[[contact]\]](mailto:[contact]) to confirm that the DSMC-approved data and statistical analyses are used appropriately.

Link to the DSMC Data Release Policies and Processes:

<https://www.cancer.northwestern.edu/docs/research/publication-policies.pdf>

15. ETHICS

15.1 Institutional Review Board (IRB) Approval

The final study protocol and the final version of the informed consent form must be approved in writing by an IRB. The site investigator must submit written approval by the IRB to Big Ten CRC AHQ before he or she can enroll subjects into the study.

The site investigator is responsible for informing the IRB of any amendment to the protocol in accordance with local requirements. In addition, the IRB must approve all advertising used to recruit subjects for the study. The protocol must be re-approved by the IRB as local regulations require.

Progress reports and notifications of adverse events will be provided to the IRB according to local regulations and guidelines.

15.2 Ethical Conduct of the Study

The study will be performed in accordance with ethical principles originating from the Declaration of Helsinki. Conduct of the study will be in compliance with ICH Good Clinical Practice, and with all applicable federal (including 21 CFR parts 56 & 50), state, or local laws.

15.3 Informed Consent Process

The site investigator will ensure the subject is given full and adequate oral and written information about the nature, purpose, possible risks and benefits of the study. Subjects must also be notified they are free to discontinue from the study at any time. The subject should be given the opportunity to ask questions and allowed time to consider the information provided.

The subject's signed and dated informed consent must be obtained before conducting any procedure specifically for the study. The site investigator must store the original, signed informed consent form. A copy of the signed informed consent form must be given to the subject.

